STUDY SYNOPSIS

Study title	MULTICENTER, NON-INTERVENTIONAL STUDY, DESCRIBING PATIENTS WITH INHERITED RETINAL DISEASE (IRD) IN FRANCE
Short title	EPI-GenRet
Sponsor	Strasbourg University Hospitals
Coordinating/Principal Investigator	Pr [name]
Collaborative partner	Novartis Pharma SAS
HUS n°	8173
ID RCB n°	2021-A01786-35
NCT	NCT05122442
Study rationale	
Genetic diagnostic testing becomes increasingly important for enhancing our understanding of the disease notably the genetics and providing the best care to the patients ("Recommendations on Clinical Assessment of Patients with Inherited Retinal Degenerations - 2016," 2016), and several initiatives seek to gather more data in order to better understand and treat those diseases.
 
Within this context, Novartis and SENSGENE/Strasbourg University Hospitals (HUS) want to set up, through a research collaboration, a non-interventional study in France to better understand the epidemiology of IRDs, particularly the distribution of pathogenic variants in patients. This study aims to serve as a starter study to implement an IRD national registry led by SENSGENE/Strasbourg University Hospitals (HUS). The data collected might also be used to populate global European registries (cf ERN-EYE initiatives). The primary objective has been defined in a sufficient broad way to address this perspective of registries.
 
As IRDs can present from birth to late middle age, this study will include both children and adult patients regardless of age, sex, and the type of IRD.

Primary Objective	The primary objective of this study is to describe the type of IRD of patients clinically diagnosed and who attended a consultation at one of participating centers from SENSGENE network over the inclusion period.
Secondary Objectives	
The secondary objectives are stated for patients with IRD who attended a consultation at one of the participating centers from SENSGENE network over the inclusion period.
 
 • To describe the genetic diagnosis 
 ○ To describe the genetic testing characteristics ○ To describe the distribution of genes and pathogenic variants (class 4 and class 5) associated with IRDs ○ To describe the distribution of variant of uncertain significance (VUS - class 3 variants) in IRD-associated genes ○ To describe the proportion of unsolved patients ○ To describe the type of pathogenic variants in each IRD-associated gene identified

	
 • To evaluate the potential correlation between the patient's genotype and the IRD phenotype • To describe the clinical characteristics • To describe the diagnosis pathway • To describe the socio-demographic characteristics of patients • To describe the therapeutic care of patients
Primary endpoint	Proportion of patients by type of IRD (based on ORPHA classification for IRD)
Secondary endpoints	
 • Proportion of patients by type of analysis performed for definitive molecular genetic diagnosis • Proportion of each type of genetic analysis performed and duration between clinical diagnosis and definitive molecular genetic diagnosis • Proportion of genes with at least 1 pathogenic variant identified (classified as class 4 likely pathogenic and class 5 pathogenic) according to transmission mode • Proportion of variants according to their classification (class 4 and 5) in a specific gene and in all IRD genes • Proportion of variants of uncertain significance (VUS-class 3 variants) • Proportion of unsolved patients • Proportion of pathogenic variants according to the: 
 ○ Mutation's nomenclature ○ Nature of gene mutation ○ Allelic status ○ Origin of the allele • Proportion of patient with family segregation assessment • Proportion of similar genotype in other family members • Proportion of "classic cases", i.e. patients whose clinical phenotype is associated with the expected genotype • Proportion of "atypic cases", i.e. patients whose clinical phenotype is associated with unusual/unexpected genotype • Proportion of patients whose type of IRD (ORPHA classification) was modified after definitive molecular genetic diagnosis • Proportion of patients by: 
 ○ Age at first symptom onset ○ Circumstances of discovery ○ Type of clinical assessments to confirm the clinical diagnosis ○ Age at date of clinical diagnosis ○ Type and number of current symptoms related to IRD at consultation ○ Associated clinical signs

	
 ○ Medical history of interest • Proportion of patients according to the values of visual acuity (VA) and visual field (VF) by patients' clinical characteristics • Proportion of patients with a cystoid macular oedema (CME) on last coherence tomography (OCT) done • Proportion of patients with preserved macular area appearance by autofluorescence at consultation • Proportion of patients according to lens status • Proportion of patients with cataract at consultation • Proportion of patients with posterior capsular opacification • Proportion of patients with cataract (phakic and pseudophakic) with an impact on VA • Proportion of patients by type of clinical assessments performed • Diagnostic odyssey (Length of time from the first symptoms onset to the clinical diagnosis and Length of time from the previous molecular genetic test and the definitive molecular genetic diagnosis for patient who already had a molecular genetic test) • Proportion of patients by age class, gender, type of occupation and geographical origin • Proportion of patients by type of treatments administered for IRD
Study design	
This study is a multicenter, cross-sectional non-interventional study that aims to set up a registry of patients with IRD in France.
 
This study relies on primary data collection and a cross sectional design. Data will be collected for both patients with prevalent IRD (patients who were already clinically diagnosed with IRD before the inclusion in the study) and patients with incident IRD (patients who were clinically diagnosed with IRD upon their inclusion in the study). To address the primary objective, all patients seen by the physician over the inclusion period following site initiation will be included into the study, on a consecutive and exhaustive basis until a maximum of 1000 patients is reached (registry starter).
 
Given the capacity of sites to screen patients over one year (around 3000 patients), the inclusion of patients into the study will be limited to the first 1000 patients in order to favor the data collection quality by limiting the sites workload. This will also encourage the inclusion of the patients exhaustively, especially for high volume sites for which this registry represents a deep work. However, it should be reminded that this study is a starter study that is planned to be extended to a larger national registry.
 
Since this study is non-interventional, nor clinical interventions neither genetic tests, imaging and assessment schedule will be

	
required as part of this study, and all data will be collected as per physicians' routine practice.
 
Patients included in this study must have either available genetic results upon their inclusion in the study (whether the result of this test is positive or negative) or a genetic testing prescription for IRD (genetic testing through PFMG platform or from a traditional reference public laboratory). Given the delay for obtaining genetic results, the data may be available within approximately 12 months after the test prescription.

Inclusion and non-inclusion criteria	
Only the patients who meet all the following inclusion criteria can be included in this study:
 
 • All patients, whatever age or gender, clinically diagnosed with IRD or with high suspicion for IRDs based on clinical examination and functional tests (such as fundus exam and ERG), regardless of genetic testing • Patients who attended a consultation at one of the participating centers from SENSGENE network over the inclusion period starting from sites initiation • Patients who had been prescribed a genetic test for IRD prior to or at the date of inclusion. • 
Patients who present at least one of the following non-inclusion criteria cannot be included in this study:
 
 • Patients/Parents/Legally authorized representatives (LAR) opposed to the collection and processing of their medical data/the medical data of their children/the medical data of the person for whom they are LAR; • Patients who are suffering from any other retinal disorder or optic neuropathy that may clinically or genetically overlap with IRD or non-genetic (phenocopy); • Patients/parents/Legally authorized representatives (LAR) refusing genetic testing; • Patients lacking decision-making capacity: Mental incapacity, unwillingness, or language barriers precluding adequate understanding or cooperation.
Conduct of the study	
French reference and competence centers for rare eye diseases are gathered within the SENSGENE network. The Filière de santé maladies rares (FSMR) SENSGENE fulfills national missions around rare sensory diseases with the aim of improving the care of patients, coordinating and encouraging research and developing training and information. Seven French reference and competence centers from the SENSGENE network will be contacted to participate in the study.
 
 • Five coordinating or constitutive reference centers for rare eye diseases: HU-Necker-Enfants Malades-APHP (Paris), CHNO XV-XX (Paris), CHI Créteil, HU Strasbourg, CHU Montpellier. • Two competence centers for rare eye diseases: CHU Nantes and CHU Lille
Required sample size	
This study will set up a registry that will include all eligible patients with IRD who attended a consultation at one of the participating centers from SENSGENE network.

	
For the Cross-sectional registry no sample size calculation is required as this registry will record patient fulfilling the sets of criteria defined and will allow to have an estimation of the target population at the national level.
 
Given the capacity of sites to screen patients over one year (around 3000 patients), the inclusion of patients into the study will be limited to the first 1000 patients in order to favor the data collection quality by limiting the sites workload. This will encourage the inclusion of the patients exhaustively, especially for high volume sites for which this registry represents a deep work. However, it should be reminded that this study is a starter study that is planned to be extended to a larger national registry.
 
The precision can be estimated for a sample size of 1000 patients while considering 5% loss (patients not evaluable for the primary objective or not meeting all selection criteria).
 
The following table presents the precision and the corresponding 2-sided 95% confidence interval (CI) to describe the distribution of IRD type (proportions varying from 10% to 50% for each modality) and a sample size of 1000 patients.
 
Table. Precision and corresponding 2-sided 95% CI given the proportion of a modality varying from 10% to 50% and a sample size of 1000 patients (5% of non-evaluable patients)
 
  
 	Proportion	
 
 10%	20%	30%	40%	50%	
   
 n	Precision	Precision	Precision	Precision	Precision	
 
 Précision (%)	1.9	2.5	2.9	3.1	3.2	
 
 95% CI	8.1; 11.9	17.5; 22.5	27.1; 32.9	36.9; 43.1	46.8; 53.2	
  
 
The precision (e) is calculated based on the normal approximation using the following formula:
 $e = \sqrt{\frac{1,96^2 * (p - p^2)}{n}}$ 
where p is the proportion of a given modality and n is the number of patients.
		Proportion					10%	20%	30%	40%	50%	n	Precision	Precision	Precision	Precision	Precision	Précision (%)	1.9	2.5	2.9	3.1	3.2	95% CI	8.1; 11.9	17.5; 22.5	27.1; 32.9	36.9; 43.1	46.8; 53.2
	Proportion																													
	10%	20%	30%	40%	50%																									
n	Precision	Precision	Precision	Precision	Precision																									
Précision (%)	1.9	2.5	2.9	3.1	3.2																									
95% CI	8.1; 11.9	17.5; 22.5	27.1; 32.9	36.9; 43.1	46.8; 53.2																									

Statistical method
	
A descriptive analysis will be conducted on all study endpoints for which data has been collected both for the overall study population and per subgroups of interest where relevant (e.g. patients' clinical characteristics, classification (class 4 and 5), nature of the mutation, the values of visual acuity (VA) and visual field (VF), date of genetic testing, clinical phenotype, type of genetic analysis performed and unsolved patients) as long as that the sizes of the sub-groups are relevant for statistical estimations. The subgroups' modalities and associated endpoints will be detailed in the Statistical Analysis Plan.
 
The following statistics will be provided for quantitative variables: number and proportion of patients with non-missing and missing
																													

	
values per variable, mean, standard deviation (StD), median, first quartile (Q1), third quartile (Q3), minimum and maximum value, the mode (especially for discrete quantitative variables with limited variability).
 
For qualitative variables, the number and proportion of each variable modality will be provided together with the number of missing values. Proportion will be computed based on the population with non-missing data.
 
Exploratory comparison between study subgroups might be considered. Statistical tests will be based on the type and distribution of the variables. All comparison tests will be two-tailed with a standard type 1 error threshold of 5% (significance level).
 
The enrollment of patients in the study will be limited to a maximum of 1000 patients, registered over a variable period of time limited to 12 months.
 
This study design therefore presents bias related to the heterogeneous duration of patients' inclusion which depends on the activity size of each participating physician.
 
In order to take into account the biases associated with this study design and be able to extrapolate results at the national level, an adjustment is planned for descriptive analyses over the registry using a weight applied at center level.

Expected benefits	
Implementation of an IRD national registry including all data related to IRD and presenting their clinical features may help to deepen the epidemiologic and genetics knowledge of IRDs. No direct benefit to the participating patient is expected from this study but the knowledge generated from this study may benefit future patients.

Provisional schedule	
 -Maximum duration of the inclusion phase: 12 months or the maximum of 1000 patients is reached, whatever occurs first (a) -Maximum duration of participation of each patient: 12 months (b) -Maximum total duration of the study: 24 months (= a+b) -Exclusion from other interventional studies while patients participate to the present clinical trial: None -End of trial: The study end corresponds to the end of the collection of gene testing results of the participation of the last subject in the study.

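### Do the gene- and variant-level endpoints need a stated counting unit, and an exemption from the centre weight, before the plan can be used?

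*Combined protocol and SAP*

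**What the plan says.** The Secondary endpoints section of the synopsis mixes units. Most entries are proportions of patients. Others are worded for genes or variants: "Proportion of genes with at least 1 pathogenic variant identified", by transmission mode; "Proportion of variants according to their classification (class 4 and 5) in a specific gene and in all IRD genes"; the class 3 (VUS) proportion; and pathogenic variants by nomenclature, nature of the mutation, allelic status and allele origin.

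The Statistical method section covers them together: "A descriptive analysis will be conducted on all study endpoints for which data has been collected". For qualitative variables its denominator rule is "Proportion will be computed based on the population with non-missing data". Because patients are included over periods of different length, depending on physician activity, and in order to "be able to extrapolate results at the national level", it adds that "an adjustment is planned for descriptive analyses over the registry using a weight applied at center level". It gives no formula for the weight and no list of the tables that carry it. It leaves the subgroup categories and their endpoints to the SAP, and it names variant class and nature of the mutation among the subgroup examples.

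The Secondary Objectives section opens by stating that the objectives concern patients with IRD, and one of them is to describe how genes and pathogenic variants are distributed.

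**The concern.** Two things look wrong.

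- **The weight.** A centre weight belongs to a patient, because each patient is enrolled at one centre. A gene, or a distinct variant, may be seen at several of the seven centres and then has no single weight. If the weight is meant for every descriptive table, the gene endpoint appears to have no valid weighted form, yet a weighted figure would be read as national.
- **The unit.** For the class 4/5 and VUS proportions, a recurrent variant could count once, once per patient or once per allele. The denominator rule speaks of a population, which does not settle how variants are counted. Two analysts could publish different shares from the same data.

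The stake is real, because the Study rationale singles out the distribution of pathogenic variants as an aim and foresees the data feeding larger registries.

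**Working it through.** **1. The plan's own figures.** The only computable figures are the half-widths under Required sample size, e = 1.96 × √(p(1−p)/n). With n = 1000 × 0.95 = 950, they are 1.91, 2.54, 2.91, 3.12 and 3.18 points for p = 10, 20, 30, 40 and 50%. These round to the stated 1.9, 2.5, 2.9, 3.1 and 3.2. The table is correct, and it concerns the primary endpoint, which is counted in patients.

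**2. How far the unit matters.** The document gives no genotype frequencies, so these inputs are assumptions.

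- *Zygosity.* Among patients with two pathogenic alleles, let a share h be homozygous (one occurrence, two alleles) and the rest compound heterozygous (two occurrences, two alleles). The homozygous share is h per allele and h/(h + 2(1−h)) = h/(2−h) per occurrence. For h = 20, 50 and 80%, the occurrence figure is 11.1, 33.3 and 66.7%.
- *Class 4 share.* If a share q of distinct class 4/5 variants is class 4, each seen once, and each class 5 variant is seen m times, the share by occurrence is q/(q + (1−q)m). With q = 20%, m = 1.5, 2 and 3 give 14.3, 11.1 and 7.7%.

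These gaps exceed the 2.5 to 3.2 points in step 1, which are cited only for scale. They are differences between distinct, legitimate quantities, not errors in one of them.

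**3. Whether the weight breaks the gene endpoint.** Take an invented registry of two centres, with weights 1 and 4, eight patients and four genes.

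- Read as genes, 3 of 4 have a pathogenic variant: 75%.
- With weights, the answer depends on how a gene seen at both centres is treated: 6/7 = 86% (minimum), 9/10 = 90% (mean), 12/13 = 92% (maximum) or 14/15 = 93% (sum). The plan contains none of these rules.
- Read as patients by causative gene, each patient keeps one weight. The three genes hold 4, 2 and 1 of the 7 patients with a class 4 or 5 variant (57, 29 and 14%). Weighted, they hold 10, 5 and 4 of 19 (53, 26 and 21%). The weight works as usual.

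**4. How much of the apparent size is weighting.** A simulated registry was used: 950 patients, seven centres, 60% solved, 100 genes with frequency proportional to 1/rank, and about 30% of genes dominant. All of these except the 950 patients and the seven centres are assumptions.

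| Share of dominant | Dominant genes commoner | Dominant genes rarer |
|---|---|---|
| Genes, unweighted | 31% | 29% |
| Genes, centre weights summed | 37% | 23% |
| Genes, largest centre weight | 33% | 27% |
| Occurrences, weighted | about 43% | about 16% |
| Occurrences, unweighted | about 43% | about 17% |

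The second and third rows use rules that the plan does not state. With equal weights, the largest-weight rule gives no shift at all. The last two rows agree, so the step from 31% to about 43% is a change of unit and owes nothing to the weight. If transmission mode is unrelated to gene frequency, summing the weights causes no mean shift.

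**5. Rare genes.** A gene carried by an assumed 0.1% of patients is seen at least once with probability 1 − 0.999^950 = 61%, against 1 − 0.999^3000 = 95% at the sites' annual screening capacity. That is a consequence of the 1000-patient cap, which the Study design section explains as a workload and quality trade-off. It says nothing about the weight.

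**The case for a change.** The strongest case for a change is this. The endpoint list writes of patients where it means patients, so its wording on genes and variants should be taken literally. The explicit deferral to the SAP covers subgroup categories only, not counting units or exceptions to weighting. The remedy would be a few lines of text.

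Part of that stands. The visible text does not give the counting unit for the class 4/5 and VUS proportions, the denominator for the VUS and gene endpoints, or the treatment of gene counts under weighting. It is reasonable to expect the SAP to say so: entries that belong to one patient can take that patient's centre weight, and gene or distinct-variant counts are reported as observed.

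The rest does not stand. A plan with no formula and no combining rule does not instruct anyone to produce a hybrid gene proportion. The weight is justified by unequal patient inclusion, so an analyst would attach it to patients. Allele-level counting could serve the class, VUS, nature, status and origin tables together, so the list does not force several incompatible units. A worry that relatives would repeat a family's variant without being linked is speculative: the endpoints already include family segregation and shared genotype in relatives.

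**Conclusion.** No change to the plan. The synopsis leaves out definitional detail for descriptive secondary tables, and analysts normally fill that gap in the SAP or table shells, with the unit shown in each table's title and denominator. With the unit stated, either version of a share in step 2 is correct for what it describes.

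The size is limited in three ways. The primary endpoint and the other per-patient proportions are untouched. No stated figure is wrong. The gaps of about 6 to 17 points in step 2 (from 20 − 14.3 = 5.7 to 50 − 33.3 = 16.7) rest on assumed genotype patterns and arise only if the unit goes unreported.

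The conclusion rests on two assumptions: that the supplied text is synopsis-level, with fuller definitions to follow, and that the weight is meant for entries that belong to a patient, as its stated reason implies. If a final SAP applied centre weights to distinct-gene counts and called the result national, that would be a fault in that SAP. This text does not require it.

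### Allele origin is summarised on non-missing data although whether it is known depends on which parents were tested, so for heterozygous dominant variants the reported de novo/maternal/paternal split can be selectively distorted

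*Combined protocol and SAP*

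**What the plan says.** Under Secondary endpoints, the stem "Proportion of pathogenic variants according to the" is followed by four breakdowns, one of which is "Origin of the allele". The unit is the variant, and no origin categories are listed. A separate, patient-level endpoint is "Proportion of patient with family segregation assessment", so the plan itself expects that not every family will have been studied.

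Under Study design, no genetic test is imposed and "all data will be collected as per physicians' routine practice". The only genetic entry condition concerns the patient's own test: "Patients who had been prescribed a genetic test for IRD prior to or at the date of inclusion".

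Under Statistical method, for qualitative variables "the number and proportion of each variable modality will be provided together with the number of missing values". The denominator rule follows: "Proportion will be computed based on the population with non-missing data". The one correction foreseen is at site level: "an adjustment is planned for descriptive analyses over the registry using a weight applied at center level".

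**The concern.** This is not ordinary missing data, because whether origin is known depends on the origin itself. Take a heterozygous dominant variant. With both parents tested, maternal, paternal and de novo origin can each be assigned. With one parent tested, the variant is classified if that parent carries it. If not, it came from the other parent or arose de novo, and it stays unresolved. One-parent families therefore add inherited variants to the non-missing set and never add de novo ones. They also add variants only from the parent who was tested.

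The published split would then partly describe who came for testing. Recruiting more patients under the same rule does not remove the effect. The centre weight does not either, since the selection operates between families within a centre. The study is meant to start a national registry and may feed European ones, so a coding rule set here is likely to be carried forward.

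**Working it through.** **The plan's own figure.** None is given for allele origin. The only statistical figure is the precision table for type of IRD under Required sample size. It reproduces to one decimal with n = 950 (1000 less 5%); for example, 1.96 × √(0.10 × 0.90 / 950) = 1.9 points. It has no bearing on this endpoint.

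**Model for one heterozygous dominant variant.** All inputs are assumptions, since the documents supply none:
- d = true de novo share; h = (1 − d)/2 = share from each parent.
- t = both parents tested; a = mother only; b = father only.
- Unresolved origin is treated as missing.

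Variants classified, as shares of all variants:
- de novo: D = d·t
- maternal: M = h(t + a)
- paternal: P = h(t + b)
- all classified: K = D + M + P

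The reported proportions are D/K, M/K and P/K.

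**Illustration 1.** d = 0.10, h = 0.45, t = 0.30, one parent tested in 0.30, of which 80% are mothers (a = 0.24, b = 0.06).
- D = 0.10 × 0.30 = 0.030
- M = 0.45 × 0.54 = 0.243
- P = 0.45 × 0.36 = 0.162
- K = 0.435
- Reported: 6.9% de novo, 55.9% maternal, 37.2% paternal, against a true 10/45/45%.

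**Illustration 2.** Same d; t = 0.20, one parent tested in 0.40 (a = 0.32, b = 0.08).
- D = 0.020, M = 0.234, P = 0.126, K = 0.380
- Reported: 5.3%, 61.6%, 33.2%.

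**Range with a true de novo share of 5% (47.5% from each parent).**

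| t, a, b | De novo | Maternal | Paternal |
|---|---|---|---|
| 0.80, 0.10, 0.05 | 4.6% | 49.1% | 46.3% |
| 0.50, 0.20, 0.05 | 4.0% | 53.7% | 42.2% |
| 0.30, 0.30, 0.10 | 3.1% | 58.2% | 38.8% |
| 0.10, 0.40, 0.10 | 1.5% | 70.4% | 28.1% |

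**If unknown origin is a recorded category.** In illustration 1 the table would read 3.0% de novo, 24.3% maternal, 16.2% paternal and 56.5% unknown (1 − 0.435). The maternal:paternal ratio is 24.3/16.2 = 1.5, the same as 55.9/37.2.

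**If two-parent testing depends on origin.** Let t′ be the two-parent rate among de novo cases, with t, a and b now applying to inherited cases. Reported de novo = d·t′ / [d·t′ + (1 − d)(t + (a + b)/2)]. The bias is zero when t′ = t + (a + b)/2. With d = 0.05, t = 0.30, a = 0.30, b = 0.10, the second term is 0.95 × 0.50 = 0.475, and:
- t′ = 0.50 (1.67 times t): 0.025/0.500 = 5.0%, no bias
- t′ = 0.60: 0.030/0.505 = 5.9%
- t′ = 0.90: 0.045/0.520 = 8.7%

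**Restriction to two-parent families.** If testing is unrelated to origin, the split returns to d, h, h. If it is not, the restricted de novo share is d·t′ / [d·t′ + (1 − d)t]. With t′ = 0.60 this is 0.030/(0.030 + 0.285) = 9.5% against a true 5%, further off than the 5.9% on non-missing data. The restricted table therefore needs its condition stated and the excluded count beside it.

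**The case against.** **The premise is not written down.** The synopsis names neither de novo nor unknown as a category. If unknown is a recorded value, the non-missing rule keeps it in the denominator and the illustrated percentages do not arise. This stands as a limit on the figures. It does not rescue the endpoint, because the maternal:paternal skew is unchanged.

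**The direction is not assured.** A reader might infer that de novo variants are bound to be under-counted. The documents do not support that. Testing follows routine practice, which may favour testing both parents when a de novo event is suspected, and the bias can then disappear or reverse.

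**The mechanism is not general.** A reader might also infer that testing the patient alone never shows origin and that one parent can only confirm inheritance. That fails in a registry of all IRD types. A homozygous variant, or an X-linked variant in a male, is informative from the patient alone. For an X-linked variant in a male, a negative mother can indicate a de novo event. In a recessive pair in trans, one parent's result can imply the origin of the other allele. Under that rule, with d = 0.05 and t, a, b = 0.30, 0.30, 0.10, the parental imbalance disappears (48.9% each), although de novo falls to 2.2%.

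**Allelic status.** It is tempting to extend the point to that breakdown. The endpoint counts variants, the zygosity of a single variant does not need phase, and the documents contain no biallelic count, so the extension is unsupported.

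**The gap is partly visible.** The number missing and the share of patients with segregation assessment will both be reported. They show that data are incomplete, but not that the loss is selective or which parent was tested.

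**Conclusion.** The concern holds for heterozygous dominant variants. With unresolved origin treated as missing and parental testing unrelated to origin, the stated denominator is expected to give too low a de novo share and too high a share for the parent tested more often. The size cannot be derived from the documents. In the illustrations a true 10% de novo becomes 6.9% or 5.3%, and a true 5% becomes anything from 4.6% to 1.5%. The de novo direction is conditional, not known.

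This is one descriptive secondary endpoint, and the primary endpoint and precision table are untouched. It should still be changed: the planned denominator gives a selectively distorted split, counting the missing values does not correct it, and the remedy is cheap.

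**What to change.** 1. Add one field to the genetic data: parents tested (both, mother only, father only, none).
2. Under Secondary endpoints, define the origin categories, including *origin not established*. For this endpoint only, replace the non-missing denominator in the Statistical method with all pathogenic variants, so that *origin not established* has its own share.
3. Present the maternal/paternal/de novo split by transmission mode among variants with both parents tested; for X-linked variants in males, among those with the mother tested. Show the number excluded beside it, and note that this subset is unbiased only if parental testing is unrelated to origin.

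No relative needs to be tested for the study. The cost is the extra field, some wording, and a smaller origin table with wider intervals. The field is easiest to capture at first data collection.
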